The Investigator, [name] has assumed Sponsor responsibility to the governing regulatory authorities to take all reasonable steps to ensure the proper conduct of the study with respect to ethics, protocol adherence, and data integrity and validity.

This single centre clinical trial will be closely monitored in real-time throughout its duration utilizing an electronic data capture (EDC) database. On-site monitoring will occur up to one time per week after first participant signs consent and is started on the study vaccine. The on-site monitoring will include 100% ICF verification and 100% source verification with electronic data entry. Continued appropriate communications will occur by email correspondence or telephone. The study monitor, Investigator and study safety lead reviews AEs in aggregate on a monthly basis. The study statistician provides study data reports to the Investigator prior to each review. The following may be assessed during monitoring:

- Regulatory documentation
- Signed ICFs
- Case Report Forms within 5 days post visit.
- Investigative product inventory records
- SDV-source data verification. Data is complete, accurate and verifiable to source documents.
- Participant accrual and follow-up visits.
- Investigator and participant compliance to the study protocol.
- Concomitant medication documentation
- Adverse event documentation
- Protocol deviation documentation

The investigator and study team are expected to cooperate with the study monitor during monitoring times and permit direct access to all relevant documents.

Audits and Inspections

All documentation relating to this clinical trial may be subject to a QA audit by the Investigator, [name], or Regulatory Authorities (Health Canada). Upon

Page 18 of 24

request, the auditor will inspect, copy, review and audit all source documents, CRFs, medical records, correspondence and signed ICFs. Other documentation subject to the audit includes the research ethics files, certifications, and quality control of supporting laboratories and pharmacies.

Data Collection

The primary tool for data collection to be used in this study will be the participant's weekly symptom diary. This will be used to gain information on any symptoms participants have experienced. This will be reviewed with the participant at each of their visits and used to help fill out the Case Report Forms (CRFs). All information collected on the CRFs will be entered into the online database by the site within 5 days of each study visit.

Data Management

A secure computer-based database will be created for the collection of study data. The study team will have access to the database and will be required to input and edit participant's data. Database access will be controlled by userspecific logins. Only the study participant's partial date of birth (month and year), with the default day of 15 will be entered into the database. There will not be any other participant identifying information entered into the database. The data will be labelled with the study participant's unique identification number (i.e. 01-01). All of the data entered into the electronic database must be supported by appropriate source documents.

Within 5 days of the completed study visit, all data should be entered into the electronic data capture system. The site is also responsible for responding to any data queries from the study monitor within 5 days of receiving the query.

Retention of Records

All study records must be kept by the Investigator for a minimum of 25 years following completion of the study as specified by Division 5 of the Health Canada Food and Drug Regulations. Records must be kept in a safe and secure location where they can be easily retrieved. All records must be kept confidential.

If the Investigator relocates, retires or withdraws for any reason from the study, trial records may be transferred to an acceptable designate within the institution.

Ethical Considerations

All study activities, procedures and assessments outlined in this protocol are designed to abide by the governing principles of the Declaration of Helsinki, consistent with ICH- GCP, Health Canada, and all other applicable laws and regulations.

Prior to starting the study, all sites must provide documented approval from the appropriate research ethics board (REB) or institutional review board (IRB).

The Investigator must report any changes in the research activity including all unexpected issues involving risks to the participant or others to the Research Ethics Board. The Investigator will supply progress reports as required to the Research Ethics Board. The Investigator is responsible for assuring continuing review and approval of the clinical trial on an annual basis. The Investigator will provide documentation to the Research Ethics Board when study participation is completed.

Written Informed Consent

The Investigator agrees to protect the rights, safety, and welfare of the participants enrolled into the trial, including obtaining written informed consent prior to performing any study-related procedures and informing each participant that the investigative product is being used for investigational purposes. A copy of the research ethics approved ICF will be used during the study.

The purpose and description of the study along with possible adverse effects must be explained to the participant prior to entry into the study. All questions should be answered to the satisfaction of the participant or participant's legal representative. The investigator or designate is responsible to obtain written informed consent from each participant thus attesting freely given consent. A copy of the signed and dated ICF will be given to the participant. Documentation of the informed consent process must be clearly indicated in the participant's clinical files and the original ICF must be available for review by the study monitor.

In the event that modifications of the experimental design, dosages, tests and assessments, etc. of the protocol are required and where potential risk to participants is increased, revisions to the ICF are also required. Such revisions will be reviewed and approved by the research ethics board and documentation of this approval will be forwarded to the Investigator for submission to Health Canada.

Any changes to the protocol will be informed of all study design modifications or increase in potential risk and written informed consent will be obtained.

Records and Case Report Forms

The Investigator is required to prepare and maintain accurate case histories designed to record all observations and other data related to the investigation on each participant treated with investigative product. Data reported on the CRF, derived from the source documents, must be consistent with the source documents, or any discrepancies must be explained.

Protocol Deviations

The study is to be conducted as described in the protocol without deviation unless there is a safety concern. The protocol must not be modified for any participant without the prior consent of the Research Ethics Board responsible at the investigative site.

Termination of the Study

If the Investigator discovers conditions during the course of the trial that indicate that the study should be discontinued an appropriate procedure for termination will be instituted.

Reasons for closure of the trial or termination of the study by the Investigator may include the following:

- Successful completion of the study at study site.
- Failure of Investigator to comply with the protocol, GCP guidelines or regulatory requirements
- Safety concerns

Rationale for Study Design

It would be difficult and really impossible to undertake a large multicenter randomized placebo controlled prophylaxis trial with limited funding. The need for evaluation of this type of intervention in Canadian female patients is unquestionable and the general efficacy and safety of Uromune® in Canadian women can be assessed using an open label real life observational study design employing using each participant's history of UTI as their own individual control. We will be able, within the number of participants planned for enrollment (convenience sample based on the number of individual Uromune® doses to be provided by supporting company) to answer our aim: To determine if Uromune therapy provides a clinically acceptable (efficacy and safety) prophylactic option in lieu of continuous and/or interval antibiotic dosing for Canadian women with a history of recurrent UTI.

We do not want to prove that this intervention is better than other interventions (in fact there are no other real non-antibiotic alternatives) but rather reduce the risk of recurrent UTI in women who are suffering from multiple UTIs requiring antibiotics. Each individual participant will be their own control based on the number of UTIs that are documented over the previous 12 months (to be included participants must meet the criteria of 3 documented UTIs requiring antibiotics over the last 12 months or 2 UTIs requiring antibiotics over the previous 6 months).

Number of Participants: Inmunotek, through its Canadian distributor, has offered the principle investigator at no cost, vaccine product (Uromune®) to treat up to 80 participants. The number of participants enrolled will be a convenience

sample based on the early UK experience [2]. It is expected that 80 participants in total (with an expected drop out rate of 15%) enrolled at the Urology Centre at Queen's University site will allow a preliminary assessment of efficacy and safety. The UK early experience study reported that 78% (59 participants of a total of 75 evaluable participants) had no subsequent UTI in the 12 months after the vaccine was administered. One participant reported a treatment related rash while <10% of participants experience mild adverse reactions with only one participant temporarily suspending treatment. We anticipate that based on this experience, 80 participants will be sufficient to determine safety and potential efficacy.

Analysis

Primary outcome: The individual participant will be considered a complete responder if they have no UTI requiring antibiotics reported in the 12 months since initiating therapy. A 50% responder rate of all enrolled participants will be considered a very clinically significant result. Based on the results from the first experience report from the UK (Yang and Foley, 2017) with Uromune® which demonstrated that 78% of the 75 women who completed treatment had no subsequent UTIs in the follow-up period, our convenience sample should be sufficient to power our analysis. The primary efficacy endpoint will be considered to have been achieved if a clinically significant and important level of more than 50% of participants undergoing therapy has no reported UTI in the 12 months after initiation of therapy.

Secondary outcome: The number of UTI in individual participants requiring antibiotics in the 12 months after starting therapy will be compared to the number of UTIs requiring antibiotics before therapy is initiated (number over previous 12 months or 2 X the number over the preceding 6 months). The analysis will include individual participant data comparisons as well as the mean number of UTI before and after initiation of therapy in the entire cohort. Based on the results from the comparison of Uromune® vs antibiotics from Spain (Lorenzo-Gomez MF et al 2012) which demonstrated a mean UTI rate after Uromune® therapy (n=136) of 0.36 (CI0.29-0.44) at 6 months, 0.72 (CI 0.60-0.85) at 9 months, the study should be adequately powered to show a statistically significant difference in our convenience sample of participants enrolled with a history of at least 3 UTI in the preceding 12 months.

Quality of life and satisfaction questionnaires will also constitute secondary endpoints

The analysis for both efficacy and safety will be an intent to treat analysis of all participants who took at least one dose of the Uromune®. A per protocol efficacy analysis will include all participants who completed the 3 month treatment regime.

Interim Analysis Plan and Stopping Rules

An interim analysis will be carried out when 50% of participants reach the 6month follow up interval. Stopping rules will be based on safety considerations – the study would be stopped if >20% (8 participants) experienced Treatment Emergent Serious Adverse Events (TESAEs). Safety will be monitored continuously for the rest of the study and the study will be stopped if at any time, if >20% of participants experience TESAEs.

Summary Statement: Rationale for this Investigator Initiated Early Experience Real Life Clinical Practice Study

We hope that this study will provide guidance for the use of Uromune® (when or if it is released in Canada) by providing information on the best way to manage recurrent UTI in individual participants using their own clinical data (in this case the number of recurrent UTI). The ultimate goal is to reduce participants' suffering (and therefore improve quality of life), participant time spent dealing with this problem, indirect costs (time off work or other activities), antibiotic use, antibiotic resistance and health care utilization (including costs). We plan to undertake this study with great enthusiasm with limited funding (and "in kind" supply of Uromune® from Red Leaf Medical) because of the huge unmet need for better preventative therapy for our Canadian women with recurrent UTI.

Responsibilities:

Principle Investigator ([name]) Responsibilities – will assume sponsor responsibilities: The PI ([name]) will be responsible for protocol development, diary and CRF development, IRB approvals, informed consent, inclusion/exclusion criteria confirmation, safety monitoring, data analysis, and presentation/publication of results..

Supplier (Red Leaf Medical) Responsibilities: Red Leaf Medical will be committed to providing Uromune® for 80 participants to be enrolled in the trial. The Supplier is not committed to provide funds to the investigator, [name] or provide any further financial support for the trial.

References:

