- Urine (midstream specimen) for urinalysis, bacterial culture and pregnancy test (if participant is of child bearing potential) will be collected.
- Review of any changes in concomitant medications.
- Reporting of any adverse events or changes in health status.
- Receive oral and written instructions for participant weekly diary use.
- Participants will receive 3 month (90 day) supply of Uromune® treatment and be given instructions on administration of study treatment. The participant will administer first dose of study treatment during this visit.
- Review of any adverse events after study treatment administration.

Participant Follow-Up:

3 Month Clinic Visit (90 days +7 from Baseline Visit):

Participants will return to the clinic for a predetermined visit following the three month (90 day) vaccine administration. During this visit participants will undergo:

- Completion of Quality of Life Questionnaire (SF-12) and Satisfaction Questionnaire prior to any other study procedures.
- Vitals (blood pressure and heart rate), height and weight.
- Urine (midstream specimen) for urinalysis, bacterial culture and pregnancy test (if participant is of child bearing potential) will be collected.
- Return of study treatment bottle.
- Diary compliance check and return of treatment period diary.
- Vaccine compliance check. This will be conducted through a review of the participant's diary.
- Reporting of any adverse events or changes in health status.
- Review of any changes in concomitant medications.
- Review of UTI history including symptoms, number of diagnosed UTIs, review of cultures performed, bacteria responsible for UTI and any treatments participant has received over the preceding 3 month period (If the participant has reported a UTI, all efforts will be made to complete the CRF with documentation of physician notes and/or culture reports if available).
- Instructions on how to complete the post treatment symptom diary.

6 Month Phone Call (+/- 7 days):

Participants will be contacted by phone 6 months after their baseline visit and asked about the following:

- Diary compliance check to ensure participant has been completing their symptom diary.
- Reporting of any adverse events and a check of health status.
- Review of any changes in concomitant medications.

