- Review of UTI history including symptoms, number of diagnosed UTIs, review of cultures performed, bacteria responsible for UTI and any treatments participant has received over the preceding 3 month period (If the participant has reported a UTI, all efforts will be made to complete the CRF with documentation of physician notes and/or culture reports if available).

9 Month Phone Call (+/- 7 days):

Participants will be contacted again by phone 9 months after their baseline visit and asked about the following:

- Diary compliance check to ensure participant has been completing their symptom diary.
- Reporting of any adverse events and a check of health status.

- Review of any changes in concomitant medications.
- Review of UTI history including symptoms, number of diagnosed UTIs, review of cultures performed, bacteria responsible for UTI and any treatments participant has received over the preceding 3 month period (If the participant has reported a UTI, all efforts will be made to complete the CRF with documentation of physician notes and/or culture reports if available).

12 Month End of Study Clinic Visit (+/- 7 days):

Participants will return to the clinic for a predetermined visit 12 months after their baseline visit. During this visit participants will undergo:

- Completion of Quality of Life Questionnaire (SF-12) and Satisfaction Questionnaire prior to other study procedures.
- Vitals (blood pressure and heart rate), height and weight.
- Urine (midstream specimen) for urinalysis, bacterial culture and pregnancy test (if participant is of child bearing potential) will be collected.
- Diary compliance check and return of post treatment period diary.
- Reporting of any adverse events and check of health status.
- Review of any changes in concomitant medications.
- Review of UTI history including symptoms, number of diagnosed UTIs, review of cultures performed, bacteria responsible for UTI and any treatments participant has received over the preceding 3 month period (If the participant has reported a UTI, all efforts will be made to complete the CRF with documentation of physician notes and/or culture reports if available).

Unscheduled Study Visit:

Should a participant return to the clinic for an unscheduled visit they will undergo the following:

- Urine (midstream specimen) for urinalysis, bacterial culture and pregnancy test (if participant is of child bearing potential) will be collected.

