To perform a midstream urine specimen collection, please instruct all participants to follow the same procedure. Participants should be given instruction to hold the labial folds open, clean the urinary opening with the provided cleaning towelette, begin urinating into the toilet and then bring the open specimen bottle into the urinary stream to collect the "midstream urine". Participants can be told to stop collecting when the specimen container is half to two thirds of the way full. They should then firmly tighten the lid on the container.

A urinalysis, urine culture and pregnancy test (if indicated) will then be performed on the midstream urine sample.

This sample will only be kept for the time period required to conduct the testing and any left-over sample will be destroyed. Samples will be analyzed by the study staff and then sent to the local lab for analysis.

Quality of Life (SF-12) and Satisfaction Questionnaires:

At each clinic visit, participants will be asked to complete the Quality of Life Questionnaire (SF-12) and the Satisfaction Questionnaire. At the beginning of the clinic visit, both questionnaires should be given to the participant and they should be given ample time to complete them prior to any other study procedures or assessments being conducted. Both questionnaires must be done before any other study related activities so as not to have any influence on the way that the participant answers the questions.

Treatment Period Diary

At the baseline visit, participants will be given their treatment period diary and receive instructions on how to complete it. This diary will be done on a weekly basis during the 90 days they are on study treatment. Participants should be instructed to complete one page of their diary at the end of each week (7 days). In the diary participants will record whether or not they have taken their vaccine every day for the past 7 days. If they have not, they will need to record how many times they did take it. The will also record any symptoms they have experienced that week. If participants do experience symptoms they will be instructed to record the past 7 days and any treatment they received. Detailed instructions for the participants can be found on the front page of the diary. Participants will return their diary at their 3 month clinic visit.

Post Treatment Period Diary

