At the 3 month clinic visit participants will receive their post treatment period diary, along with instructions on how to complete it. This diary does not need to be completed at any specific time. From the 3 month visit until their 12 month end of study visit, participants will be instructed to fill out this diary only when they experience a symptom. They will record the date of their symptom, what symptom they experienced, any medical attention they sought and any treatment they received. Detailed instructions for the participant can be found on the front of the diary. Participants will be asked about this diary at their 6 and 9 month follow up phone calls and they will return their diary at their 12 month end of study visit.

Study Treatment

Description of Investigational Product

The investigational product, Uromune®, being used in this study will be supplied by Immunotek, Spain to Red Leaf Medical in Mississauga, Ontario. Red Leaf Medical will distribute the investigational product. Properties and characteristics of Uromune® can be found in the Investigators Brochure.

9mL vials of the investigational product will be shipped from Red Leaf Medical to the investigator, [name]. Should the site require additional vials of study treatment they will be required to contact Red Leaf Medical. Participants will be provided with 9 mL vials of Uromune® treatment. This will be enough to last participants the 3 month treatment period (90 days).

Packaging

The investigative product will be packed in a sterile topaz glass vial, closed with a white plastic swivel top containing a spray insert. Each vial will contain 9 mL of Uromune®. Sufficient quantities will be dispensed to enable the participant to continue to take the study medication up to the next study visit.

Labelling

Each bottle will be labelled in accordance with all applicable regulatory requirements.

Storage

Authorized study staff will supply the study treatment to participants. All investigational products must be stored in a secure and locked location where only the investigator and study staff may access it.

The investigative product is to be stored in its original packaging in order to protect it from light. It is to be kept refrigerated at 5 (± 3) degrees Celsius without excursions. It is important not to freeze the product.

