The Principle Investigator provides oversight of the study with assistance from the research coordinator. One of the purported advantages of sublingual administration is greater safety, which allows for administration of this treatment outside of the medical setting.

First dose will occur in medical setting and research coordinator will monitor and record any adverse reactions. Participants will be provided with specific instructions as to how to administer treatment at home and advised to call the research coordinator if bothersome adverse events are experienced. If a dose is missed the participant is not to make up missed dose but resume next scheduled dose. Additionally, the research coordinator will follow-up with each participant within one week of start of treatment to assess any adverse reactions.

The PI will review all study data and any adverse events in real time and reports all SAEs to the study monitor, study safety lead, research ethics board as per local guidelines. AEs are assessed at each study visit by the study team or during review of hospital chart at hospital admission.

All AEs will be assessed and therapeutic strategies implemented according to medical opinion of the PI. Additionally, SAEs will be assessed by the study safety lead.

Occurrence of a UTI

Should a study participant experience a UTI throughout the course of the trial, it will not be captured as an AE. The UTI, along with the symptoms, medical attention and treatment received will be captured through the participant's diary and recorded in the electronic data capture system.

The Investigator must submit sufficient initial information to Health Canada should the SAE report meet the criteria (serious, unexpected and possibly or related to study treatment) for completion of an Adverse Event Drug Reaction Expedited Reporting Summary form and CIOMS report.

As much of the following information about the participant and the event will be requested:

- Participant study code, gender, age, or date of birth
- Underlying diagnosis and extent of disease
- Lot number and expiration date of study drug
- Date of last study drug administration
- Date of death (if applicable)
- Intervention required
- Concomitant medications
- Pertinent laboratory data
- Pertinent medical history
- Study drug status (dose interrupted, discontinued)

- Did event abate after interruption of study drug administration (if applicable)
- Did event recur after study drug was reintroduced (if applicable)

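### For 9 of the 12 endpoint months the diary is filled in only when symptoms occur, so a missed contact plus a blank diary would pass as UTI-free

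*Combined protocol and SAP*

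**What the plan says.** The Data Collection section states: "The primary tool for data collection to be used in this study will be the participant's weekly symptom diary". The section on the occurrence of a UTI says that UTIs are not recorded as adverse events. The UTI, with its symptoms and treatment, "will be captured through the participant's diary" and then entered in the database.

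There are two diaries. Of the first, the Treatment Period Diary section says: "This diary will be done on a weekly basis during the 90 days they are on study treatment". Each weekly page also records vaccine intake, so a completed page without symptoms is a positive statement that nothing happened. Of the second, covering the 3 month to the 12 month visit, the Post Treatment Period Diary section says "This diary does not need to be completed at any specific time" and that "participants will be instructed to fill out this diary only when they experience a symptom". It is handed back only at the 12 month visit.

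The diary is not the only source. The 6 and 9 month calls and the 12 month visit each include "Review of UTI history including symptoms, number of diagnosed UTIs, review of cultures performed, bacteria responsible for UTI" and treatments, over the preceding 3 months, plus a review of changes in concomitant medications. Physician notes and culture reports are sought if the participant has reported a UTI. Both calls also include a "Diary compliance check to ensure participant has been completing their symptom diary".

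Under Analysis, a responder has no antibiotic-treated UTI reported in the 12 months from the start of therapy. The primary endpoint is met if more than 50% of participants respond.

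**The concern.** The primary endpoint is the absence of a reported event, so anything unrecorded counts toward success. During treatment, a weekly page separates a woman who was well from one who stopped recording. After Month 3 the diary cannot do this, because an empty booklet is what both women would return. The compliance check at the calls has no stated criterion for a diary that may properly be empty, and staff cannot see the booklet by telephone.

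The plan does not say how a blank diary, a missed call or incomplete follow-up is classified, although it expects 15% dropout and analyses everyone who took at least one dose. At stake is an upward bias in the responder rate of an open-label, single-arm study judged against a fixed 50% line. The secondary before-and-after comparison of UTI counts would be biased in the same favourable direction.

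**Working it through.** **Share of the window.** Months 3 to 12 are 9/12 = 75% of the endpoint period; in days, (365 − 90)/365 = 75.3%.

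**What covers each post-treatment quarter**

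| Quarter | Diary | Scheduled UTI history |
|---|---|---|
| Months 3–6 | symptom-triggered | 6 month call |
| Months 6–9 | symptom-triggered | 9 month call |
| Months 9–12 | symptom-triggered | 12 month visit |

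If all contacts take place, every woman is asked directly about each quarter. If the 6 month call is missed, the 9 month history as worded reaches back only to Month 6, and Months 3–6 rest on the symptom-triggered diary. The medication review has no stated look-back and might pick up an antibiotic course, but nothing requires it to. Even with no missed call, the ±7 day windows allow 3 months plus 14 days between the 6 and 9 month calls, against a 3 month look-back.

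**Sensitivity of the responder rate.** The plan gives no miss rate and no true responder rate for this cohort, so both are assumed. Take a constant UTI rate with a 12-month mean of λ, Poisson counts, and a share q of Month 3–12 UTIs never recorded by any route:

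observed UTI-free rate = exp{−λ[0.25 + 0.75(1 − q)]}

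- λ = 0.75: true rate exp(−0.75) = 47.2%. With q = 10%, exp(−0.69375) = 49.97%, or 50.0% rounded. With q = 20%, exp(−0.6375) = 52.9%.
- λ = 0.80: true rate 44.9%. With q = 20%, exp(−0.68) = 50.7%.
- True rate 78%: λ = −ln 0.78 = 0.2485. With q = 20%, exp(−0.2485 × 0.85) = 81.0%.

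**Dependence on the model.** Two alternatives bracket the Poisson figures:

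- Geometric counts, 1/(1 + m[0.25 + 0.75(1 − q)]) with m = 1/p − 1, where p is the true rate.
- Misses clustered by woman, where a share q of women record nothing after Month 3: (1 − q)p + q·exp(−0.25λ).

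| True rate, q | Geometric | Poisson | Clustered |
|---|---|---|---|
| 47.2%, 10% | 49.2% | 50.0% | 50.8% |
| 47.2%, 20% | 51.3% | 52.9% | 54.4% |
| 44.9%, 20% | 49.0% | 50.7% | 52.3% |

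**Effect on the decision.** With 80 participants, more than 50% means at least 41 responders. Let u be the share of true non-responders whose every UTI goes unrecorded, so that the observed rate is p + (1 − p)u. Exact binomial probabilities of meeting the rule are:

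| True rate | u = 0 | u = 10% | u = 20% |
|---|---|---|---|
| 40% | 0.027 | 0.203 | 0.598 |
| 45% | 0.156 | 0.491 | 0.834 |
| 78% | >0.999 | >0.999 | >0.999 |

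**Secondary outcome.** Under the constant rate, q = 20% lowers the 12-month mean count by 0.75 × 20% = 15%, whatever λ is.

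**The case against.** The strongest reply is that the diary only helps to fill in the case report forms. Every woman is asked at Months 6, 9 and 12 how many UTIs were diagnosed and how they were treated, and her medications are reviewed separately, which matters because the endpoint is an antibiotic-treated UTI. To be lost, an event must escape the diary, the UTI history and the medication review together. The baseline comparator is itself a reported history over 6 or 12 months. No planned analysis compares the treatment quarter with the later ones, so the change of diary format does not distort a comparison between periods. The diary's front-page instructions and the case report forms are not in the supplied text and may already hold a yes/no field.

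Most of this stands, and it rules out stronger readings that a reader might infer. One is that the trial cannot tell a woman with a blank diary from a UTI-free woman. That is true of the booklet alone, not of a trial that questions her every three months. Another is that the compliance checks have nothing to check. Staff can ask about the diary, and a UTI reported by telephone but absent from the diary would expose non-completion. What they cannot do is verify a negative.

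The reply does not cover a missed contact. All three routes are self-report, the UTI history reaches back only 3 months, and outside records are sought only once a UTI has been reported.

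**Conclusion.** The point holds in limited form. The diary descriptions conflict, and for 75% of the endpoint window a blank diary is not evidence of no UTI. With all contacts completed, the remaining weakness is unverified recall. With a missed contact and a blank diary, the literal responder definition counts an unobserved period as UTI-free, and that error can only raise the responder rate.

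The size cannot be estimated from the documents. It could matter if the true rate is just under 50%: with 10% to 20% of later UTIs missed, 47.2% becomes 50.0% to 52.9% under the Poisson assumption. The 10% case reaches the line without exceeding it. The starting rates were chosen close to the line and the miss rates are assumptions, so these figures show sensitivity and are not a forecast. A reader might take them as upper limits because they assume that no missed event is recovered, but misses clustered by woman give higher values. A reader might also infer that a positive result would be unsafe in general. The documents do not support that: near the cited 78% the conclusion does not change. This is a worthwhile, inexpensive correction and not a fatal flaw.

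**What to change.** 1. Add a dated monthly entry to the post-treatment diary: no UTI treated this month, or UTI treated with details. Have participants read the entries out at the 6 and 9 month calls, since staff cannot see the booklet until Month 12.
2. Run each UTI-history review from the last completed contact, with an explicit yes/no for antibiotic-treated UTI. This closes the gap after a missed call and any gap created by the visit windows.
3. State that a month with neither a diary entry nor a contact answer is unobserved, not UTI-free, in the primary analysis. Report the number of women affected, and the responder rate with them counted first as non-responders and then as responders.
4. Reconcile the Data Collection, Occurrence of a UTI and Post Treatment Period Diary sections so that they describe two diaries and name the source that determines the endpoint in Months 3 to 12.

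The cost is nine short entries per woman and a few minutes at each call. The entries remain self-report and could be filled in late, but they replace a presumed negative with a recorded one.
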